Therapeutic abortions, as well as spontaneous miscarriages, can lead to a variety of complications. Most complications are considered minor such as pain, bleeding, infection, and post-anesthesia complications, while others are major, namely uterine atony with subsequent hemorrhage, uterine perforation, injuries to adjacent organs (bladder or bowels), cervical laceration, failed abortion, septic abortion, and disseminated intravascular coagulation (DIC).(**Carlsson, et al. 2018**)

Cervical ripening means thinning, softening and opening of the cervix. Various pharmacological& non pharmacological methods are available for cervical ripening each having its own advantages& disadvantages.(**Moustafa, et al. 2019**)

Misoprostol is a synthetic prostaglandin E1 analogue which was originally developed to prevent non-steroidal anti-inflammatory drugs related gastric ulcers. However it has been used for various other indications in obstetrics and gynaecology.(**Anderson, et al. 2009**)

Nitric oxide is a potent inflammatory intercellular mediator and signaling molecule. Nitric Oxide causes relaxation of smooth muscle that induces vasodilatation of both arteries and veins causing venous pooling of the blood. It was known for its effect as an endothelium-derived relaxing factor and a primary regulator of blood pressure. Several recent studies have shown that it is involved in several aspects of female reproductive physiology, including the process of cervical ripening. Nitric oxide is less effective than prostaglandin analogues, but has fewer adverse effects (**Mousioli, et al. 2013**).

There is an additive effect of the cervical ripening effects of nitric oxide donors and that of prostaglandins. The combination therapy allows a small dose of

nitric oxide donor to be given in combination with a small dose of prostaglandin to affect the cervical ripening. The advantage of such strategy is reducing the side effects associated with larger doses of either agent used alone(Arteaga et al. 2005).

6. Objectives:

The aim is to compare the therapeutic efficacy of prostaglandins when they used alone versus a combination therapy of prostaglandins and isosorbide-5-mononitrate to induce cervical ripening and effacement for induction of the first trimester missed abortion .

7. Study Design:

- Randomized Clinical Trial

8. Study Methods

- Population of study

All women who had first trimester missed abortion will be asked to participate the study

Group A (n = 30) will receive only vaginal Misoprostol 800mcg (4 tablets Cytotec 200mcg)(Pfizer)every 3 hours to a maximum of two doses or until reaching cervical ripening.

(The doses of Misoprostol will follow the New FIGO Guidelines for Misoprostol use 2017)

Group B (n = 30) will receive combined vaginal Misoprostol 800mcg (4 tablets Cytotec 200mcg) every 3 hours to a maximum two doses with Isosorbide-5-

mononitrate 20 mg (Effox20 mg)(MINAFARM) once at the beginning with misoprostol(**Athanasios Mousiolis et al., 2012**)

- **Study setting:**

Embaba General Hospital Obstetrics and Gynaecology Department

- **Inclusion criteria:**

- Maternal Age 18 - 35 years.
- Gestational age first trimester of pregnancy (between 5-13 weeks).
- Missed abortion confirmed by ultrasound.
- Singleton pregnancy.
- Normal uterus and cervix on clinical examination.
- Cervix is not dilated.
- No vaginal bleeding.

- **Exclusion criteria:**

- Evidences suggesting start of spontaneous abortion and previous trial to induce abortion.
- Presence of uterine contraction or bleeding,
- Multi-fetal pregnancy.
- Suspicion of septic abortion.
- History of Previous cervical surgery or manipulation. Ex: cervical tear , cervical cauterization .
- Uterine anomaly.
- Presence of IUD in situ.
- Underlying medical diseases.Ex:DM,HTN
- History of allergy or adverse effects to vaginally administered medication e.g. isosorbide -5- mononitrate
- Those unwilling to participate in the trial
- Higher order cesarean section(more than three)

- **Methodology in details:**

All Patients will be informed about the study and will be included in the study after their approval and will be subjected to :

1- Consent :

Written consent will be obtained from the pregnant women who are included in the study after explanation of the study and its aims, for performing surgical evacuation for any remnants if needed .

2- Full History Taking :

- Name
- Maternal Age
- Obstetric history (Gravidity and parity)
- First day of last menstrual period
- Gestational Age
- Medical and surgical history
- Previous laparotomies and their types
- Previous Pregnancy complications
- History of smoking
- Pelvic pain

3- Clinical Examination :

- Height(in cm) and weight(in kg) measurements, BMI calculation
- Blood pressure measurement
- Bimanual Examinations (PV Examination)
- Previous scars analysis

4- Laboratory investigations :

- Preoperative and postoperative CBC
- Coagulation profile
- Kidney and liver functions
- Blood sugar level
- Investigation:

All women will undergo Trans-abdominal or Trans-Vaginal Ultra-sonography during the routine examination to confirm the inclusion criteria of the study (gestational age and confirmation of missed abortion)

The patients will be allocated into 2 groups using computer-generated

randomization:

Group A (n =30) will receive **only** vaginal Misoprostol 800mcg (4 tablets Cytotec 200mcg)) every 3 hours to a maximum of two doses or until reaching cervical ripening or uterine contractions or bleeding assessed by the same doctor who made evaluation at the beginning.

Group B (n =30) will receive combined vaginal Misoprostol 800mcg (4 tablets Cytotec)) every 3 hours to a maximum of two doses or until reaching cervical ripening or start of uterine contractions or bleeding.

with Isosorbide-5-mononitrate (20 mg).

Effox 20 mg)once at the beginning with misoprostol until reaching cervical ripening or start of and uterine contractions assessed by the same doctor who made the evaluation at the beginning.

- **Intervention:**

Therapeutic intervention

No intervention

- **Does the research involve?**

Human participants

Biological samples/Tissues

Identifiable private data/Information

- **Potential risks:**

- 1- Complication of nitric oxide donor : Throbbing headache, postural hypotension , nausea, vomiting, sweating, flushing.
- 2- Complication of prostaglandin agent: abdominal pain, diarrhea, fever, rupture uterus.

allergic reaction, chills.

- **Confidentiality of data:**

- All study-related information will be stored secured at the study site.
- All participant information will be stored in locked file cabinets in areas with limited access.
- Participants, study information will be not released outside of the study without the written permission of the participant.

9- Study outcomes

- **Primary outcomes** (Most important measurable outcomes)

Induction to abortion interval: the Duration interval between the beginning of the induction and beginning of cervical ripening assessed by cervical examination(cervix become soft and start to dilate) and uterine contractions leading to complete expulsion of the abortus spontaneous and if cervical ripening isn't occur by maximum doses the investigators will make surgical evacuation.

and also the Number of the doses of misoprostol needed to complete expulsion (spontaneous or surgical)when prostaglandins used alone and when prostaglandins and a nitric oxide donor used together .

- **Secondary outcome parameters** (other outcomes to be assessed)

Association between adverse events that increased or newly discovered when prostaglandins and a nitric oxide donor used together such as severe bleeding , headache, abdominal pain, pelvic pain, sever hypotension , backache, fever, nausea and vomiting .

10- Sample size

Sample size calculation was done using the comparison of induction to abortion interval in women with missed first trimesteric abortion treated with vaginal misoprostol combined with isosorbide mononitrate compared to those treated with misoprostol alone. As reported in previous publication (***Yehia and El ansary H 2020.***),, the mean \pm SD of induction to abortion interval in combined group was approximately 10.7 ± 12.8 h, while in misoprostol alone group it was approximately 20.9 ± 13.8 h. Accordingly, the investigators calculated that the minimum proper sample size was 30 participants in each group to be able to reject the null

hypothesis with 80% power at $\alpha = 0.05$ level using Student's t test for independent samples. Sample size calculation was done using PS Power and Sample Size Calculations software, version 3.0.11 for MS Windows (William D. Dupont and Walton D., Vanderbilt University, Nashville, Tennessee, USA).

11- Statistical analysis

The collected data using patient sheet form will be coded, entered on Excel sheet and analyzed using statistical package for social sciences (SPSS) Using appropriate statistical test, with a p value less than 0.05 considered as statistically significant, P value more than 0.05 Insignificant.

A descriptive statistics will be done using frequency distribution table, graphs, means, standard deviations, median and range, or frequency and percentage.

12- Source of funding:

- Faculty of Medicine, Cairo University
- Other sources:

Please specify: **Self-funding**

13- Time plan:

- When to start march 2021
- When expected to finish September 2021
- When to publish?

14- References:

- ❖ Anderson, J., E. Gouk, L. Young, L. Turnbull, G. et al(2009). ("P420 A randomised controlled trial of oral versus vaginal misoprostol for medical management of early fetal demise)." *International Journal of Gynecology & Obstetrics* **107**: S533-S533.

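### The first primary outcome is named for abortion but defined to end at onset of ripening; its end event is ambiguous, and the stated 80% power belongs to the abortion interval only

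*Protocol*

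**What the plan says.** All references are to the protocol.

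- **Section 9, Primary outcomes.** The first primary outcome is "Induction to abortion interval: the Duration interval between the beginning of the induction and beginning of cervical ripening". Ripening is judged by examination, as softening and the start of dilatation. The same sentence continues with "uterine contractions leading to complete expulsion of the abortus spontaneous". It then adds that where ripening does not "occur by maximum doses the investigators will make surgical evacuation".
- **Section 9, second primary outcome.** This is the "Number of the doses of misoprostol needed to complete expulsion", and it counts expulsion achieved either spontaneously or surgically.
- **Section 6, Objectives.** The aim is stated in terms of ripening and effacement of the cervix, as a means to induce the abortion.
- **Section 8, Study Methods.** Misoprostol is given "every 3 hours to a maximum of two doses or until reaching cervical ripening". The fuller description of the arms later in that section adds contractions or bleeding as reasons to stop. Expulsion is not named as one.
- **Section 10, Sample size.** "Sample size calculation was done using the comparison of induction to abortion interval". The "induction to abortion interval in combined group was approximately 10.7" h (SD 12.8 h), "while in misoprostol alone group it was approximately 20.9" h (SD 13.8 h). The result is 30 per group for 80% power at alpha 0.05 with Student's t test. No planning figure is given for time to ripening.

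**The concern.** A cervix that has begun to soften and dilate is not an abortion, so the name and the first clause of the definition describe different events. Two assessors could record different times for the same woman and both comply with the protocol.

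Three things are at stake. First, a positive primary result would be hard to interpret, because an effect on onset of ripening need not equal an effect on time to expulsion. Second, the stated power was calculated for one of these events only. Third, if the end event is settled after the data are seen, the choice could follow the result. The protocol itself fixes the definition, its name and its sample size, so this is not a detail that can be left to a separate analysis plan.

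**Working it through.** **1. Reproduce the planned sample size.** Inputs from section 10: means 10.7 h and 20.9 h, SDs 12.8 h and 13.8 h, alpha 0.05, power 80%, t test, equal groups. Sidedness is not stated, so two-sided is assumed; one-sided versions give 20 to 23 per group and do not match.

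- Difference: 20.9 − 10.7 = 10.2 h.
- Normal approximation: n = 2 × (1.960 + 0.842)² × (SD / difference)². With SD 13.8 h this is 2 × 7.85 × (13.8 / 10.2)² = 2 × 7.85 × 1.830 = 28.7, so 29 per group.
- Exact calculation with the noncentral t distribution, SD 13.8 h: 29.7, so 30 per group. Power is 80.4% at 30 and 79.0% at 29.
- Pooled SD = √((12.8² + 13.8²) / 2) = √177.14 = 13.31 h: 27.7, so 28 per group. Power at 30 is 83.1%.

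The 30 per group is therefore correct for the induction to abortion interval on the stated inputs.

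**2. Ask which event ends the interval.** The protocol's statements divide as follows.

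| Points to ripening | Points to abortion or expulsion |
|---|---|
| Definition, first clause (section 9) | Name of the outcome (section 9) |
| Failure rule leading to evacuation (section 9) | Second primary outcome (section 9) |
| Objective (section 6) | Sample size (section 10) |
| Dosing stop (section 8) | |

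The running-on clause of the definition can be attached in three ways:

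- The interval ends at onset of ripening, and the rest describes what follows.
- It ends when both ripening and contractions have begun, with expulsion describing what the contractions lead to.
- Ripening and contractions describe the process, and expulsion ends it. This agrees with the name but contradicts the sentence's own reference to the beginning of ripening.

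**3. Ask what power applies to ripening.** The calculation needs the difference divided by the SD. For the abortion interval this is 10.2 / 13.8 = 0.74. For ripening the protocol gives neither quantity, so power cannot be computed. As an illustration only, with an assumed SD of 3 h and 30 per group, power is 25%, 72% and 97% for assumed differences of 1, 2 and 3 h. The answer could fall well below or well above 80%.

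**The case against.** The strongest reply is that the definition must be read as a whole. It goes on to complete expulsion, the outcome is named for abortion, and section 10 uses the same name. On that reading there is one event throughout and the sample size fits it. This reading is possible, and for that reason the fault is an ambiguous end event in conflict with its name, not a definition that settles on ripening. It does not remove the problem: it is strained against the sentence's own wording, and the objective, the dosing stop and the failure rule all turn on ripening.

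The protocol also does not show how the cited publication defined its interval. That stands. The mismatch rests on this protocol's wording alone.

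A reader might infer that the trial is underpowered for ripening, because two doses 3 h apart leave a short window in which group means could hardly differ by 10.2 h. The documents do not support this. The hour at which failure to ripen is judged is not stated. A short window would also limit the SD: if it were 6 h (an assumption), the SD could be at most about 3 h. The same standardised effect of 0.74 would then need only about 0.74 × 3 = 2.2 h.

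On surgical evacuation, the second primary outcome does treat surgical completion as completion. No such statement is made for the interval. How these women are handled in the analysis may properly sit in an analysis plan that is not at hand; what ends their interval is part of the definition.

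**Conclusion.** The concern holds as a conflict within the protocol. The first primary outcome carries the name of one event, its definition opens with another, and onset of ripening, onset of contractions and expulsion can all be read as its end. The 30 per group has 80.4% power for the abortion interval (difference 10.2 h, SD 13.8 h, two-sided 0.05 assumed). For time to ripening the stated 80% has no basis and no figure can be computed. Whether 30 per group is too few or too many for that event cannot be determined.

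The evidence does not settle which event the sponsor intends. Since this is the primary outcome, it has to be resolved, and preferably before outcome data are examined by group.

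**What to change.** Reconcile sections 9 and 10 by naming one end event.

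- **If complete expulsion**, which matches the name and the sample size: delete the reference to the beginning of ripening from the primary definition. Report time to ripening as a secondary outcome, since the objective names it.
- **If ripening**, which matches the objective: rename the outcome, and restate the planning mean, SD and power in section 10 for that event.
- **In either case**: state in the definition what ends the interval for women who go to surgical evacuation.

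The cost is a short amendment to section 9, and to section 10 if ripening is chosen. In that case new planning figures must be found and the sample size could change. If expulsion is chosen and its time is not already on the patient sheet, which is not shown, it may have to be retrieved for women already enrolled; the planned start was March 2021.

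### The primary interval has two different end events, leaves the handling of surgically evacuated women unclear, and no listed outcome shows the rate of expulsion without surgery

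*Protocol*

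**What the plan says.** Protocol section 9, Primary outcomes, names an induction-to-abortion interval. It defines it as the "interval between the beginning of the induction and beginning of cervical ripening" and continues, within the same sentence, to "uterine contractions leading to complete expulsion of the abortus spontaneous". The sentence closes with the clause "if cervical ripening isn't occur by maximum doses the investigators will make surgical evacuation".

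A second primary outcome follows: the "Number of the doses of misoprostol needed to complete expulsion (spontaneous or surgical").

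The secondary outcome is given as "Association between adverse events that increased or newly discovered when prostaglandins and a nitric oxide donor used together", followed by an open list of symptoms and events. Neither the proportion of women who expel completely without surgery nor the proportion evacuated is listed.

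Three other places bear on the reading:

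- Section 6 (Objectives) states the purpose as comparing efficacy "to induce cervical ripening and effacement for induction of the first trimester missed abortion".
- Section 8, under Consent, foresees surgery on a second ground: "for performing surgical evacuation for any remnants if needed".
- Section 10 (Sample size) is worked on the induction-to-abortion interval, with mean 10.7 h (SD 12.8) for the combination and 20.9 h (SD 13.8) for misoprostol alone, using Student's t test.

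**The concern.** The start of ripening and complete expulsion happen at different times, and nothing says which one stops the clock. The rest of the protocol points both ways. The outcome's name and the planning figures fit expulsion, while the objective and the trigger for evacuation fit ripening.

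The women who matter most for efficacy are those in whom the drug did not work. They reach neither event, and the sentence that sends them to surgery does not say what value they take. If they are left out, the comparison is restricted to responders. If their time of evacuation is entered, an early evacuation looks like a fast success.

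The dose count does not make up for this, because it merges spontaneous with surgical completion. Two analysts could both follow the text, report clearly different effects from the same data, and neither would have to report how often treatment failed.

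**Working it through.** **1. The plan's own figure.** Inputs from section 10: difference 20.9 − 10.7 = 10.2 h, SDs 13.8 and 12.8, 80% power, α = 0.05 (two-sided assumed), Student's t test.

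- With SD 13.8, the noncentral-t calculation gives 30 per group, with power 80.4%.
- With the pooled SD, √((12.8² + 13.8²)/2) = 13.31, it gives 28 per group, and power at 30 is 83.1%.

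The stated 30 per group reproduces. It presumes that every woman contributes an interval.

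**2. Who has an interval under each reading.**

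| Woman | Clock stops at ripening | Clock stops at expulsion | Clock also stops at evacuation |
|---|---|---|---|
| Ripens, expels completely | yes | yes | yes |
| Ripens, evacuated for remnants | yes | no complete spontaneous expulsion | yes, at evacuation |
| No ripening, evacuated | none | none | yes, at evacuation |

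The status of the last two rows depends on a choice that the text does not make.

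**3. Dose count.** Suppose that in each arm 12 of 30 women finish after one dose and 18 after two. The mean is (12×1 + 18×2)/30 = 1.6 doses in both arms. It stays 1.6 whether 9 of those 18 (30% of the arm) or 3 of them (10%) were evacuated. The equal split is chosen for the example. The point is that the score cannot separate the two cases.

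**4. Interval, expulsion reading (illustration).** The protocol gives neither failure rates nor an evacuation time. Assumed: failures in 30% on misoprostol alone and 10% on the combination, with evacuation at c hours. The value c = 6 h stands for doses at 0 and 3 h plus one further 3-hour interval.

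*Failures at random, evacuation time entered:* difference = (0.7×20.9 + 0.3c) − (0.9×10.7 + 0.1c) = 5.0 + 0.2c.

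- c = 6: 6.2 h
- c = 12: 7.4 h
- c = 24: 9.8 h

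*Slowest women fail, evacuation time entered:* with log-normal times matched to the planning means and SDs, the fastest 70% on misoprostol alone average 14.01 h and the fastest 90% on the combination average 7.52 h. At c = 6 the difference is (0.7×14.01 + 0.3×6) − (0.9×7.52 + 0.1×6) = 11.61 − 7.37 = 4.2 h. Gamma times also give about 4.2 h. At c = 12 it is about 5.4 h, and at c = 24 about 7.7–7.8 h.

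*Failures dropped:* random failures leave 20.9 − 10.7 = 10.2 h. If the slowest fail, the log-normal result is 14.01 − 7.52 = 6.5 h and the gamma result 6.3 h, so about 6.4 h.

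*Failure rates the other way round* (10% on misoprostol alone, 30% on the combination, random, c = 6): (0.9×20.9 + 0.1×6) − (0.7×10.7 + 0.3×6) = 19.41 − 9.29 = 10.1 h. The interval would look almost exactly as planned although the combination failed three times as often.

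**5. Power of the t test in these scenarios.** It is 82–84% with no failures. With evacuation entered at 6 h it is 47–54% for random failures, and roughly 63–85% if the slowest fail, depending on the distribution and on how failures are drawn. Entered at 12 h with the slowest failing, it is 91–99%. There is no single direction.

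**The case against.** The strongest reply is that the protocol does deal with evacuated women. Evacuation stands inside the sentence that defines the interval, and the dose outcome openly accepts surgical completion, so the interval could simply end at evacuation. This stands in part. A reader might infer that these women have no interval at all, and the text does not support so firm a statement; their handling is unclear. But the reading offered in defence is the one that scores a failure as a time to success.

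A second reply is that the sizes are assumed. They are. The failure rates, evacuation times and distributions are not in the protocol, and the planning means are attributed to a reference whose title concerns second-trimester abortion. No magnitude can be given for ripening against expulsion as the end event, because the protocol has no data on it. The figures show sensitivity, not an expected bias.

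A third reply is that section 11 provides for frequencies and percentages, the adverse-event list is open, and an analysis plan may settle the method. It is true that evacuations could be tabulated, and that the choice of method can be left to the analysis plan. The end event, the pooled dose count and the list of outcomes are, however, fixed in this document.

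The dosing rule is weak support for the ripening reading. One version runs "every 3 hours to a maximum of two doses or until reaching cervical ripening", but the fuller version under the methodology also stops at contractions or bleeding.

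**Conclusion.** The point holds and should be corrected before the data are analysed. One primary interval has two end events, women evacuated for want of ripening reach neither, the dose count treats failure and success after two doses alike, and no listed outcome is the rate of expulsion without surgery. These conclusions rest on the wording alone.

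The sizes rest on the assumptions stated. Under failures of 30% and 10%, the planned 10.2 h difference lies anywhere from about 4.2 h to 10.2 h according to how evacuated women are entered and which women fail.

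Three stronger inferences are not supported:

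- A reader might assume that every woman who has not expelled by some fixed hour is evacuated, which would nearly erase the difference at 6 h. The stated trigger is absence of cervical ripening, not absence of expulsion.
- A reader might conclude that the sample size is wrong or that power is lost. The 30 per group reproduces, and power can move either way.
- Nothing here shows that the direction of the result would reverse.

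**What to change.** 1. Reconcile the primary definition to one end event. Expulsion fits the outcome's name and the planning figures; ripening fits the objective and the evacuation trigger. The investigators should choose and use the same event throughout.
2. Keep all 60 randomised women in the comparison. Count surgical evacuation for failure as a failure, neither dropped nor entered as a completed interval. Worst ranking, or a competing event in a time-to-event analysis, would both serve; the choice and its power can be left to the analysis plan.
3. List complete expulsion without surgery, by arm with a confidence interval, as a descriptive outcome. State how women evacuated for remnants are classed, and report the dose count separately for spontaneous and surgical completion.

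Items 1 and 3 are changes of wording and should need little or no new data. Item 2 has a price: the main result may no longer be a simple difference in mean hours. The failure-rate comparison will also be imprecise at this size. For example, 9/30 against 3/30 is a 20-point difference with a 95% interval (Newcombe) from −0.5 to 39 points, and Fisher's exact test has 37% power for 30% against 10%. That is why it is proposed as descriptive. No change to dosing or to the rule for evacuation is proposed.

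### Two outcomes are named primary, but the trial is sized and tested as if there were one, and no rule says whether one or both must succeed

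*Protocol*

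**What the plan says.** Protocol section 9, under the plural primary heading, defines the interval as "the Duration interval between the beginning of the induction and beginning of cervical ripening". The same sentence goes on to "uterine contractions leading to complete expulsion of the abortus", and adds that if ripening does not occur "by maximum doses the investigators will make surgical evacuation". A second primary outcome follows: "and also the Number of the doses of misoprostol needed to complete expulsion". Secondary outcomes are listed separately and consist only of adverse events, so the dose count cannot be read as secondary.

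The dose count has a narrow range. In section 8, misoprostol in Group A is given "every 3 hours to a maximum of two doses or until reaching cervical ripening or uterine contractions or bleeding", and Group B has the same cap of two doses.

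Section 10 uses the interval only: 10.7 (SD 12.8) h in the combined group against 20.9 (SD 13.8) h with misoprostol alone, Student's t test, alpha 0.05, 80% power. On that basis "the investigators calculated that the minimum proper sample size was 30 participants in each group". It makes no assumption about doses.

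Section 11 sets one threshold for all tests, "with a p value less than 0.05 considered as statistically significant". It gives no order of testing and no division of alpha.

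**The concern.** Section 10 spends the whole 0.05 on one test, while section 9 gives a second outcome the same rank and section 11 the same threshold. The protocol neither states nor excludes that a significant dose count alone would make the trial positive.

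Two consequences follow, depending on a rule the protocol does not give:

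- **Either outcome suffices.** There are two chances of a false positive at 0.05 each. A trial with a null interval could be reported as positive on an outcome for which it was never sized.
- **Both are required.** The error rate is not inflated, but the 80% is the power for the interval, not for success of the trial.

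**Working it through.** **1. The plan's own sample size.** Inputs from section 10: difference 20.9 - 10.7 = 10.2 h; SDs 13.8 and 12.8; pooled SD = sqrt((13.8² + 12.8²)/2) = 13.31. Sidedness is not stated, so two-sided is assumed.

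Normal approximation with SD 13.8: n = 2 × (1.96 + 0.84)² × 13.8² / 10.2² ≈ 28.7, so 29 per group. The exact t-test calculation gives 29.7, so 30 per group. The stated 30 is reproduced. Power at 30 per group is 80.4% (SD 13.8) or 83.1% (pooled SD).

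**2. Either suffices: benchmark.** With two independent tests that each hold exactly 5%:

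1 - 0.95² = 0.0975, or 9.75%.

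For two correlated normal test statistics (bivariate normal) the rate falls as the correlation rises:

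| Correlation | 0 | 0.5 | 0.8 | 0.9 | 1 |
|---|---|---|---|---|---|
| Error rate | 9.75% | 9.1% | 7.8% | 7.0% | 5.0% |

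**3. Either suffices: a one-or-two dose count.** The count is discrete and probably linked to the interval, so it was simulated under no treatment effect. There were 30 women per group and 40,000 trials per setting, with normal or lognormal times and Student's t test on the interval. A woman had one dose if a latent ripening time, correlated with the interval, fell below the quantile set by the one-dose share. The protocol gives no value for the share, the link, the shape of the times or the test for doses, so all four are assumptions. Probability that at least one p is below 0.05, no surgical evacuation:

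| One-dose share | Link | Fisher | Uncorrected chi-square |
|---|---|---|---|
| 20-80% | 0.5 | 6.0-7.5% | 8.4-9.6% |
| 20-80% | 0.8 | 5.7-6.9% | 8.0-8.9% |
| 20-80% | 1.0 | 5.2-6.4% | 7.1-8.3% |
| 5-10% | 0.5-1.0 | 4.1-6.1% | 6.6-10.2% |

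If the latest 10% are evacuated (two doses, no interval in the t test), the 20-80% rows become 6.1-7.5% and 7.8-9.7%. The simulation standard error near 5% is sqrt(0.05 × 0.95 / 40,000) ≈ 0.1 percentage points, so the lowest Fisher figure at shares of 20-80% is hardly distinguishable from 5%.

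**4. Both required.** The chance that both tests are significant cannot exceed the smaller of the two separate chances.

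- Under no effect it is therefore at most 5%; the simulation gave at most 2.2%.
- With an effect, power for success is at most the interval's 80.4% (SD 13.8). It equals that only if the dose test is significant whenever the interval test is. How far below it lies cannot be computed from the protocol, which gives no dose data.

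**The case against.** **The rule may be in the statistical analysis plan.** An order of testing is often left to that plan, which is not at hand, and sizing on the first-listed outcome is compatible with testing it first. This stands in part: the three sections are not a flat contradiction. But the protocol itself fixes two primary outcomes, one of them without a sample size basis, and one threshold for both. The ranking belongs in section 9.

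**The outcomes are nearly the same thing.** Dosing stops at ripening, contractions or bleeding, so a positive link is likely and 9.75% is a benchmark, not an expected value. This also stands. A reader might infer that the trial runs at nearly 10% error, or above 5% in every case. The protocol supports neither: no either-suffices rule is stated, and Fisher's test with a one-dose share of 5-10% gives about 4-6%. A strong link does not remove the problem in general, however, because a count of one or two is a coarse cut of a continuous time.

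**Joint power.** A reader might derive a specific joint power from section 10's means and SDs, by taking one dose to mean an interval under 3 h. The protocol does not support that. Normal times with mean 10.7 and SD 12.8 put about 20% of the combined group below zero (10.7/12.8 = 0.84 SDs above zero). Dosing also stops at ripening, contractions or bleeding, not at expulsion, so a woman may have one dose and a long interval. All that can be said is that no power basis is given for doses.

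**The double end event is a separate defect.** It is a matter of definition, not of multiplicity. It matters here only because the fix relies on the interval's stated power.

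**Conclusion.** The point holds in a limited form. Section 9 names two primary outcomes, section 10 sizes one, and sections 9 to 11 give no rule for combining them. The sample size of 30 per group is not wrong for the test it describes.

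Under an either-suffices reading, error usually exceeds 5%, by an amount that ranges from negligible to about double, depending on the dose test, the one-dose share and the link. Under a both-required reading there is no excess error, and the stated 80% is only a ceiling for the chance of success, at the SD that reproduces the sample size.

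This should be changed before analysis, because the choice between the two readings could otherwise be made after the results are known. It does not invalidate the design.

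**What to change.** In section 9, do one of the following:

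- name the interval as the single primary outcome, tested at two-sided 0.05, and make the number of doses the first secondary outcome; or
- keep both in a fixed order: the interval at 0.05, then doses at 0.05 only if the interval is significant.

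Either takes two or three sentences, removes the inflation and keeps 30 per group. The downside is that the dose count can no longer support a positive conclusion on its own.

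An equal split of alpha (0.025 each) would let it do so, but at a cost. At 30 per group the interval's power falls to 71.2% (SD 13.8) or 74.6% (pooled SD). Restoring 80% needs 37 per group (36.1 rounded up) or 34 (33.7 rounded up).

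With either recommended option, the two end events in section 9, the start of ripening and complete expulsion, must also be reconciled into one. The sponsor should state which event lies behind the means and SDs in section 10. The 80% power for the interval stands only if the two agree; otherwise section 10 needs figures for the event chosen.
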